5.3. Description of Intervention

5.3.1. Stepped PC Arm

Patients who have been randomized to the stepped PC arm will be scheduled for an initial visit with the PC clinician either in person or via secure video visit within four weeks of enrollment. During step 1, additional visits with the PC clinician will be scheduled at clinically relevant points in the patients’ illness. In our recent study, we observed that over 80% of clinic visits that the PC clinicians recorded as “significant interactions” occurred after patients’ cancer progressed or a recent hospitalization. Therefore, during step 1, patients will be scheduled to meet with the outpatient PC clinician either in person or via secure video visit within four weeks after a change in cancer treatment (including radiation), or within four weeks of discharge from an inpatient admission. ‘Change in treatment’ for this study is defined as:

- i. A change in cancer treatment due to either progression or toxicity
- ii. A discontinuation of cancer treatment

Furthermore, if a step 1 patient is hospitalized within the first four weeks of enrollment, or if an inpatient admission occurs at any time, step 1 patients will default to the

procedure for hospitalizations and a PC appointment will be scheduled within four weeks of discharge. While hospitalized, step 1 patients may have inpatient PC appointments at the discretion of their oncology team, and such appointments will otherwise have no impact on study procedures.

In our recent study, the early integrated PC intervention group had a median of seven PC visits per patient by week 24. Examining rates of cancer progression and hospitalizations from this study, we estimate that stepped care patients on step 1 of the intervention will have a median of three PC visits per patient by week 24, representing an approximate 60% reduction in PC resource utilization. If a patient is unable to be scheduled in person or via secure video visit within four weeks of the change in treatment or hospitalization, the PC clinician will attempt to contact them by telephone within the four weeks, document the call in the EHR, and the visit will be scheduled as soon as possible. If patients miss any scheduled PC visits during step 1, and the visit cannot be rescheduled within four weeks of the change in treatment or hospitalization, the PC clinician will attempt to contact the patient by telephone within seven days from the missed visit, document the call in the EHR, and the visit will be rescheduled as soon as possible. If the patient is unable to be reached by phone, the PC clinician will document the attempted contact or voicemail in the EHR. If the PC clinician does not speak Spanish, visits for Spanish-speaking patients will be conducted with the assistance of an interpreter or family member. During step 1, PC clinicians will attempt to communicate with oncology regarding what occurred in each visit, either by phone, email, personalized electronic communication, or in person.

Step 1 patients will complete the FACT-L every six weeks for a minimum of 12 months and up to 18 months from enrollment. FACT-L scores will be used to determine which step 1 patients need to step up to PC visits every four weeks. A 10-point change in the FACT-L is considered the upper range of a clinically meaningful difference and correlates with outcomes such as disease progression.⁵⁵ Therefore, we will use a ≥ 10 -point decrease in the FACT-L from baseline at any follow-up time point to transition patients to step 2 of the intervention. In our recently completed trial of early integrated PC, 30% of patients receiving usual oncology care alone experienced a ≥ 10 -point decrease in the FACT-L from baseline to week 12 with an additional 11% experiencing a ≥ 10 -point decrease at week 24. For this trial, given that patients in step 1 will have intermittent visits with PC clinicians to help with symptoms and QOL, we anticipate that substantially fewer than 40% will have a ≥ 10 -point decrease on the FACT-L by week 24, necessitating transition to step 2 of the intervention.

Patients who transition to step 2 will then meet with the PC clinician either in person or via secure video visit at least every four weeks for the remainder of their illness and be seen by the inpatient PC team if they are hospitalized. If a patient is unable to be scheduled within four weeks from the last contact, the PC clinician will attempt to contact them by telephone (and document the call in the EHR) to maintain contact at least every four weeks. If patients miss a scheduled PC visit, and the visit cannot be rescheduled within four weeks of their previous contact, the PC clinician will attempt to contact them via telephone within seven days from the missed visit and document the call

in the EHR. If the patient is unable to be reached by phone, the PC clinician will document the attempted contact or voicemail in the EHR. If the PC clinician does not speak Spanish, visits for Spanish-speaking patients will be conducted with the assistance of an interpreter or family member. For some short or weekend admissions or brief admissions for a planned medical procedure, it may not be feasible for PC to see the patient; if we are aware of a planned admission for a medical procedure or of a planned brief admission we will attempt to consult with the patient's outpatient PC provider to see if it would be beneficial for them to see PC during the brief admission.

A study staff member will score the FACT-L within 5 business days of receiving the surveys. Step 1 patients whose FACT-L scores are found to decrease by ≥ 10 -points from baseline at any time during the study will be transitioned to Step 2 for the remainder of their illness. As outpatient PC is an available service at participating institutions, we will not deny patient or oncologist requests for additional PC visits for patients assigned to step 1. However, these visits will only be scheduled upon request and they will not trigger regularly scheduled visits every four weeks. In our prior study, only one-third of patients randomized to standard oncology care received a PC consultation based on request from the oncologist or the patient, with a median of 2 visits by 24 weeks. As step 1 patients will have PC visits at clinically relevant points in their illness, we anticipate few requests for additional PC visits for patients on step 1 of the stepped care intervention. For patients who are still on step 1 at 18 months from enrollment, PC scheduling will be at the discretion of their PC and oncology teams. Patients on Step 2 surviving greater than 18 months will be permitted to decrease the frequency of PC visits as per the discretion of their PC and oncology teams. Once patients are on hospice study visits will end, and further PC care will be per standard practice.

5.3.2. Early Integrated PC Arm

Patients assigned to early integrated PC will follow the identical study procedures used in our previous and ongoing trials.^{6,34} Specifically, patients will meet with the PC clinician either in person or via secure video visit within four weeks of enrollment and at least every four weeks throughout their course of illness. If a patient is unable to be scheduled in clinic within four weeks from the last contact, the PC clinician will attempt to contact them via telephone (and document the call in the EHR) to maintain contact at least every four weeks. If patients miss a scheduled PC visit, and the visit cannot be rescheduled within four weeks of their previous contact, the PC clinician will attempt to contact them by telephone within seven days from the missed visit and document the call in the EHR. If the patient is unable to be reached by phone, the PC clinician will document in the EHR that the PC team has attempted to contact the patient or they have left a voicemail asking for a return call if there are issues needing to be addressed. If the PC clinician does not speak Spanish, visits for Spanish-speaking patients will be conducted with the assistance of an interpreter or family member. The inpatient PC team will follow patients assigned to early integrated PC when they are hospitalized. For some short weekend admissions or brief admissions for a planned medical procedure it may not be feasible for PC to see the patient; if we are aware of a planned admission for a medical procedure we will consult with the patient's outpatient PC provider to see if it would be beneficial for them to see PC during the brief admission. Patients on the early integrated PC arm

surviving greater than 18 months will be permitted to decrease the frequency of PC visits as per the discretion of their PC and oncology teams. Once patients are on hospice study visits will end, and further PC care will be per standard practice.

5.3.3. Palliative Care Intervention Delivery

While the study protocol details the frequency of contact with a PC clinician, a variety of uncontrollable factors may impact intervention delivery. Patient factors include a change in their cancer treatment schedule, cancellation of cancer treatment, or fatigue that prohibits participation in a visit. Clinician factors include clinic delays leading to missed patient appointments and insufficient staffing, especially due to meetings and vacations. To reduce patient and clinician burden, we will conduct PC visits either in-person or via an institution-approved secure video platform. If an in-person or video visit cannot be scheduled, PC visits may be conducted via telephone. We will document missed contacts as minor violations and institute a corrective action plan if more than 15% of all planned patient contact with PC does not take place per study protocol at a study site.

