3.0. Research Subject Selection

We will recruit 510 patients with advanced lung cancer receiving their care at Massachusetts General Hospital, Duke Cancer Center, or University of Pennsylvania Abramson Cancer Center to participate in a multi-center, non-inferiority randomized trial of stepped PC versus early integrated PC. Patients will be randomized in 1:1 fashion and stratified by site (MGH vs. Duke vs. Penn) and underlying diagnosis (NSCLC vs. small cell lung cancer and mesothelioma). As patients with NSCLC have a significantly better prognosis than those with small cell lung cancer or mesothelioma, we will stratify by the underlying diagnosis to ensure adequate and balanced representation between the two study groups.

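### The 15% missed-contact trigger pools both arms at a site, so it can mask a stepped-arm shortfall well above 15% when miss rates differ between arms

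*Protocol*

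**What the plan says.** Protocol 5.3.3 (Palliative Care Intervention Delivery) records each missed contact as a minor violation. The condition for a corrective action plan is worded as follows: "if more than 15% of all planned patient contact with PC does not take place per study protocol at a study site". The documents give no other numeric threshold for delivery of PC contacts.

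The expected volume of contact differs by arm. Protocol 5.3.1 reports that in the recent trial "the early integrated PC intervention group had a median of seven PC visits per patient by week 24". Its estimate for the new arm is this: "stepped care patients on step 1 of the intervention will have a median of three PC visits per patient by week 24". It puts the resulting saving at roughly 60%. A stepped-arm patient whose FACT-L falls by 10 points or more moves to step 2, with visits "at least every four weeks for the remainder of their illness". On how many will do so by week 24, the protocol says "we anticipate that substantially fewer than 40% will have a" fall of that size. Allocation is 1:1 and stratified by site (Protocol 3.0), so the arms should be about equal in size at each site.

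Monitoring is described in Appendix 9.12. The safety monitoring committee (SMC) reviews visit adherence from each site twice a year, with no split by arm and no threshold stated. Its yearly by-group summaries cover non-serious adverse events, retention and dropout, not missed PC contacts.

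**The concern.** A pooled percentage is a weighted average, with weights set by each arm's share of planned contacts. The arm with few planned contacts moves it little. Here that is the experimental arm, whose step 1 visits are placed after a treatment change or a hospital discharge because, according to 5.3.1, over 80% of the visits recorded as significant in the prior study followed progression or hospitalization. The contacts on which the stepped model most depends therefore weigh least in the rule that is meant to protect delivery.

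Two consequences follow.

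- A site could deliver stepped PC poorly without being required to produce a corrective action plan, and it would be harder to say whether the trial tested stepped PC as designed.
- The number of outpatient PC visits is a secondary superiority outcome (SAP sections 6 and 9; counted through week 24 under addendum item 3). A missed stepped-arm visit lowers that count and so looks like a saving. Without by-arm delivery rates, planned savings and non-delivery cannot be told apart.

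**Working it through.** **Inputs.** I = 7 integrated contacts per patient by week 24 and S = 3 stepped contacts on step 1 (Protocol 5.3.1); 1:1 allocation within site (3.0); threshold 15% (5.3.3). As a check on the inputs, (7 − 3)/7 = 57%, which agrees with the protocol's approximate 60%.

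**Assumptions.** The medians are used as mean planned contacts, the arms are equal in size, and only contacts to week 24 are counted.

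**Share of the denominator.** 7/(7 + 3) = 70% integrated, 30% stepped.

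**Formula.** With miss rates m_I and m_S, the pooled rate is (m_I·I + m_S·S)/(I + S). The largest stepped miss rate that does not exceed 15% pooled is

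m_S = [0.15 × (I + S) − m_I × I] / S.

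**Results with I = 7.**

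| Stepped mean S | Integrated misses 0% | 5% | 10% | 15% |
|---|---|---|---|---|
| 3 (step 1 only) | 1.50/3 = 50% | 1.15/3 = 38% | 0.80/3 = 27% | 15% |
| 4 (some step-up) | 1.65/4 = 41% | 1.30/4 = 33% | 0.95/4 = 24% | 15% |
| 5 (more step-up) | 1.80/5 = 36% | 1.45/5 = 29% | 1.10/5 = 22% | 15% |

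The 50% cell sits exactly on the limit: 1.5/10 = 15.0%, which is not more than 15%.

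**How far step-up might raise S.** The protocol gives no stepped-arm mean that includes step 2, so this is an assumption: one initial visit plus two over 24 weeks on step 1 (1/12 per week), then one visit every four weeks (1/4 per week) from step-up at week t, for a proportion p of patients. Then S = 3 + p × (24 − t) × (1/4 − 1/12).

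- p = 10%, t = 18: S = 3.1, and with no integrated misses the limit is 0.15 × 10.1/3.1 = 49%.
- p = 40%, t = 6: S = 4.2, and the limit is 0.15 × 11.2/4.2 = 40%.

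On this model S = 5 goes beyond what the protocol expects, so that row is on the cautious side.

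**Six integrated contacts instead of seven.** If the four-weekly schedule is counted as 6 by week 24, then with S = 3 and no integrated misses the limit is 0.15 × 9/3 = 45%.

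**The other direction.** If only the integrated arm misses contacts, the rule fires once it misses more than 0.15 × 10/7 = 21%. The pooled rule is looser than 15% for either arm alone, but much looser for the stepped arm.

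**The case against.** **The headline figure is a corner case.** A reader might infer that a site can miss half of all stepped-arm visits unnoticed. The documents do not support that. The 3 is a median for patients on step 1, not for the whole stepped arm; the 7 is an observed median from an earlier trial, not a planned count; and 50% needs no integrated misses and no step-up at all. With S above 3, half missed exceeds 15% pooled and the rule fires. Step 2 visits also continue beyond week 24, so the stepped share of contacts may rise and the masking shrink. All of this stands, and 50% can be given only as an upper bound.

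**Miss rates may not differ much.** The causes listed in 5.3.3 (fatigue, treatment schedule changes, clinic delays, staffing) are not specific to an arm, and telephone visits can stand in. At equal miss rates the pooled rule works as intended. This limits how often masking would occur, but the protocol has no by-arm figure that would show whether it does.

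**Missed visits are not ignored.** A reader might also infer that stepped-arm patients are left without a safeguard. That is not so. Each missed contact is logged as a minor violation; 5.3.1 requires a telephone attempt and rescheduling; step 1 patients complete the FACT-L every six weeks and can step up; and requested visits are not refused. Fidelity review (5.5.3), weekly site meetings (5.5.4), yearly case audits (Appendix 9.12) and the general site-performance provisions (Appendix 9.13) add further oversight. These answer the patient-level worry. None sets a delivery threshold by arm, and raw visit counts cannot reveal missed step 1 visits because the number planned depends on each patient's events.

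**Direction of bias.** Poor delivery of stepped PC would be expected to work against showing non-inferiority on QOL, whereas poor delivery of the control favours it. A trigger more sensitive to the control arm can therefore be defended for the primary aim. But a by-arm rule gives nothing up: if the pooled rate exceeds 15%, at least one arm's rate must, so the by-arm rule fires whenever the pooled one does. It also tightens the control arm's own limit from 21% to 15%.

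**Conclusion.** The concern holds as a gap in monitoring. The trigger is pooled, the integrated arm supplies most of the planned contacts, and when miss rates differ a stepped-arm shortfall well above 15% need not prompt site-level action. The tolerated shortfall is at most 50%, about 36–41% with a stepped mean of 4–5 contacts, 27–38% with integrated misses of 10–5%, and about 22–33% with both. It falls to 15% when both arms miss equally.

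The figures rest on medians standing in for mean planned contacts, on equal arms and on the first 24 weeks. The documents do not say whether planned inpatient PC contacts count in the denominator or how frequent they would be; counting more of them in the integrated arm would raise the limit.

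What is at stake is corrective action at site level and the interpretation of delivery and of the PC-visit outcome, not an absence of follow-up for the individual patient. The SAP (version 1.0, 06-Oct-2023) describes enrollment and intervention delivery in the past tense, so there may be little delivery left to correct. By-arm reporting keeps its value, not least because the SAP makes per-protocol analyses conditional on considerable non-adherence (section 8, Analysis Population) without saying how much that is.

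**What to change.** In Protocol 5.3.3, apply the existing 15% threshold separately to each randomised arm at each site, with step 1 and step 2 taken together for stepped PC, and start the corrective action plan if either arm exceeds it. Show missed-contact percentages by arm in the SMC's twice-yearly adherence report and in the trial report, beside the PC-visit outcome.

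The cost is about one sentence in the protocol and one extra split of data already logged. The downside is somewhat more corrective action plans, and noisier percentages at a site early in accrual. No visit schedule or step-up rule changes.

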5.4. Data Collection

Table 1 depicts the assessments, measurements, and time points for the data collection. We will administer patient-reported measures for 48 weeks from enrollment. We selected a longer administration period in the current study as the median survival for patients with lung cancer is now approximately one year. The study assessment battery takes approximately 20 minutes to complete.

Table 1. Summary of data collection instruments and time-points.

Self-Report Measure	Baseline	Every 6 weeks*	Week 12	Week 24	Week 36	Week 48
Demographic Questionnaire	X					
Self-Administered Comorbidity Questionnaire (SCQ)	X					
Functional Assessment of Cancer Therapy-Lung (FACT-L)*	X	X*	X	X	X	X
Patient Health Questionnaire-9 (PHQ-9)	X		X	X	X	X
Prognosis and Treatment Perceptions Questionnaire (PTPQ)	X		X	X	X	X
Brief Cope	X		X	X	X	X
EuroQol – 5 Dimension (EQ-5D)	X		X	X	X	X
Support Service Utilization Item					X	

*Step 1 patients will complete the FACT-L every 6 weeks for a minimum of 12 months and up to 18 months from enrollment

5.4.1. Data from Electronic Health Record:

Clinical information regarding tumor type (NSCLC, small cell lung cancer, and mesothelioma), current treatment regimen, date of diagnosis of incurable disease,

previous diagnosis of early stage disease, tumor genotype, and ECOG Performance Status will be collected at baseline.

Health care utilization data will be collected after death or at 12-months from the date the last patient enrolled on the study. We will collect data on: (1) outpatient and inpatient PC visits; (2) chemotherapy and radiation therapy administration; and (3) emergency department, hospital and intensive care unit admissions. EOL care measures will include referrals to and length of stay on hospice and location of death.

5.4.2. PC Cost and Resource Utilization Data:

PC clinicians will report which domains they addressed during the study visit and the duration of the visit after each patient encounter, using REDCap. In our MGH trial, all PC clinicians completed REDCap entries after their clinical interactions for over 99% of their encounters.⁵⁹ We will use the identical successful study procedures to ensure documentation of all PC clinical interactions in this trial. Specifically, prior to the study start all participating PC clinicians will be trained on the use of the REDCap survey and

the importance of entering this data. For each study patient encounter, the study staff will send a secure email with the patients' name and a link to the REDCap system. PC clinicians will receive an email after the visit to remind them to complete the data entry. If the PC clinician does not complete the REDCap entry, they will continue to receive periodic reminders until the end of the 4-week window. We will not accept REDCap entries more than four weeks later than the appointment date. While we have trained study sites to complete these surveys after each patient encounter, it is not feasible for them to complete 100% of this documentation. As such, we will not consider missed REDCap surveys from the PC clinicians to be protocol violations.

5.4.4. Data Storage:

All patient information and study source documents, including but not limited to signed informed consent forms, completed eligibility checklists, and participant questionnaires, will remain confidential and be scanned and stored on secure Partners computers and in REDCap. Since these records necessarily contain patient identifiers, only study staff will have access to them. Study staff will scan completed source documents, which may include identifiers such as participant names, upon their completion. Location, time, and date of the scanning of the document will be recorded. After the source document is scanned and the corresponding electronic document is confirmed to be legible, it will be collected and destroyed immediately. Study staff will destroy the original copy of the source document by following MGH procedures of destroying documents with Personal Health Information (PHI). Data abstracted from the EHR in Section 5.4.2 will be maintained in REDCap. REDCap is a free, secure, HIPAA-compliant web-based application hosted by the Partners HealthCare Research Computing, Enterprise Research Infrastructure & Services (ERIS) group. Vanderbilt University, with collaboration from a consortium of academic and non-profit institutional partners, has developed this software toolset and workflow methodology for electronic collection and management of research and clinical study data. Data collection projects rely on a study-specific data dictionary defined by members of the study staff with planning assistance from Harvard Catalyst and The Harvard Clinical and Translational Science Center EDC Support Staff. The iterative development and testing process results in a well-planned data collection strategy for individual studies. REDCap provides flexible features that can be used for a variety of research projects and provides an intuitive interface to enter data with real time validation (automated data type and range checks). The system offers easy data manipulation with audit trails, reports for monitoring and querying participant records, and an automated export mechanism to common statistical packages (SPSS, SAS, Stata, R/S-Plus).

